7.0 Study Design and Procedures

7.1 Study Design

Describe and explain the study design.

This research will utilize a randomized controlled trial (RCT) design. As this research includes three parenting programs, Incredible Years, PAT, and SafeCare, three RCTs will be conducted simultaneously. Randomization will occur at the site level to reduce the potential for contamination; as such, recruited parents will not be informed of the randomization process. When sites agree to participate (i.e., be randomized) they agree to implement the evidence-based parenting program plus the added module as they would typically implement the parenting program. Although the module is not evidence-based, they are agreeing to deliver as if it were standard procedure.

This section describes the design and procedures for the three RCTs: (1) *Incredible Years RCT*; (2) *Parents as Teachers RCT* and (3) *SafeCare RCT*. However, there are commonalities between the three trials:

- There will be two groups of providers— one assigned to deliver the parenting program and one assigned to deliver the parenting program plus additional SPSHK module at the end of the last session (described below), in support of the research question.
- Parents in the control group will complete assessments at four time points: pre-parenting intervention, post-parenting intervention, one-week post parenting, and one month post-intervention.
- Parents in the experimental group will complete assessments at four time points: pre-parenting intervention, post-parenting intervention, post-module, and one month post-intervention.
- For the experimental group, fidelity monitoring procedures will also occur in sessions for each enrolled provider-subjects. Parents and provider-subjects of these sessions will each complete a fidelity assessment instrument. With the parent’s permission, the provider will audio record two experimental sessions.

Different measures will be asked at specific assessment periods:

Measure Name (file name in supporting documents attachments)	Construct	Timing of Delivery (by Protocol Section description paragraph)
Alabama Parenting Questionnaire (APQ; ‘Measure_APQ.docx’)	Parenting behaviors and responding to child’s externalizing behaviors: subscales of Parental Involvement, Positive Parenting, Inconsistent Discipline Practices	7.2.1, 7.2.3, 7.2.5, 7.2.6

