7.2.1 Pre-parenting Intervention Assessment

Provide a description as defined above and format accordingly.

As described above, parents are recruited to participation in the research after independently signing up to participate in Incredible Years, Parents as Teachers, or SafeCare, and the agency/site providing their parenting program would have already agreed to randomization (and experimental condition providers received their training in the SPSHK module). Following consent and before any intervention has occurred, the parents will be given a paper copy of the assessment. A member of the research team will distribute surveys (identified only by a unique code—see Section 9) at the beginning of the first session to parents who have consented to participate.

The assessment is given in a booklet format. At this assessment point, parent survey booklets include the APQ, AUDIT, CES-D, DAST, ISEL-SF, READI-SF, a demographics questionnaire, and the module assessment of parents’ attitudes, knowledge, and behaviors of CSA prevention (measures described above in Section 7.1). Providers in the group sessions (Incredible Years) will engage with parents who do not wish to participate separately at this time.

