8.2 Sample size determination

If applicable, provide a justification of the sample size outlined in section 8.1 – to include reflections on, or calculations of, the power of the study.

Parents as Teachers and SafeCare

In a two-arm RCT, sample size is determined by power and estimated effect size. We are doing a repeated measures design (4 assessments), so this must be accounted for in the sample size calculation. Assuming a desired power of .8 and estimated effect of .45, the sample size needed to detect an effect at alpha .05 is 62 individuals per group ($N = 124$) for each trial. That is, 124 participants for Parents as Teachers and 124 participants for SafeCare.

Incredible Years

Because the additive approach of our research is novel, we are relying on prior CSA prevention and general PE program research to estimate the effect size. A meta-analysis of general PE programs, from which CSA programs were excluded, found the estimated average effect size for trials including a control group to be $d = .3$. A meta-analysis of CSA-specific prevention programs (Davis & Gidycz, 2000) reported the average effect size for a single session program to be $d = .59$. Averaging these findings, we estimate the effect size of our module to be $d = .45$. The group-based delivery of IY requires the experimental design to be a cluster RCT and, as such, clustering must be considered in sample size calculation (i.e.,

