participants are nested within groups). In order to calculate the required sample size for the cluster randomized trials, we used the sample size calculation equation (Equation 1) for repeated measures from Heo and colleagues (2009; Equation 19, p. 385). Cluster sampling introduces a less precise estimate of parameters than simple random sampling (e.g., commonalities among participants); this increase of variance is estimated in the design effect ($2f$). Our design has repeated measures, which introduces autocorrelation (C_f); for our purposes we estimate this to be .7. Together, the design effect and the autocorrelation of the outcome of interest over time creates the corrected design effect ($2fC_f$), estimated to be 8.0025 for our calculation. Assuming $\alpha = .05$, $\beta = .80$, 10 participants per group (N_2), 3 measurement occasions (N_1), and an effect size (Δ) of 0.45, the number of groups needed per condition (N_3) is 11; this is in agreement with simulated sample sizes presented by Heo et al. (2009; Table 1). To account for participant attrition and lack of participation in research, **we will recruit 14 groups per condition such that our sample is comprised of ~ 280 participants (140 per condition).**

Equation 1.

$$N_3 = \frac{2fC_f(\phi^{-1}(1 - \frac{\alpha}{2}) + \phi^{-1}(1 - \beta))^2}{N_2N_1\Delta^2}$$

Fidelity

Other research indicates that two audio recorded sessions from 100 provider-subjects will be sufficient to answer fidelity research questions.

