8.3 Statistical methods

Describe the statistical methods (or non-statistical methods of analysis) that will be employed.

We will be examining the effect of our module using a variety of statistical methods. Exact models to be used will be dictated by recruitment and participating sites (e.g., potentially controlling for nesting). Statistical methods considered will include simple t-tests, general linear regression models, or hierarchical regression models. We are powered for repeated measure ANOVA between factors.

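### PAT and SafeCare: the test named as powered averages two pre-module assessments with two post-module ones, so the stated 80% does not apply to it if the module effect appears only after the module; no post-module contrast is fixed

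*Combined protocol and SAP*

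**What the plan says.** Section 8.2 sizes PAT and SafeCare at 62 per group (124 per trial) for power .8, effect .45 and alpha .05. On the repeated measurements it says "We are doing a repeated measures design (4 assessments), so this must be accounted for in the sample size calculation". It gives no formula, correlation or sidedness for these two trials. The Incredible Years part of 8.2 describes .45 as the estimated effect of the module and, on the correlation over time, says "for our purposes we estimate this to be .7".

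Section 8.3 leaves the analysis open: "Exact models to be used will be dictated by recruitment and participating sites". It lists t-tests, linear regression and hierarchical regression as candidates, then states "We are powered for repeated measure ANOVA between factors".

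Section 7.1 gives the experimental arm's assessments as "pre-parenting intervention, post-parenting intervention, post-module, and one month post-intervention" (T1 to T4 below). Section 7.2.1 places T1 before any content: "Following consent and before any intervention has occurred, the parents will be given a paper copy of the assessment". Section 7.2.4 has the module delivered the week after T2, with T3 immediately after it. Section 7.1 also describes the module as coming at the close of the last session, but it still lists T2 ahead of the post-module assessment.

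Section 1.1 has two hypotheses: improvement between pre-test and post-test in parents who receive the module, and higher scores than in parents who receive only the parenting program. Section 1.2 names the project's own Module Assessment as the primary outcome.

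**The concern.** The between-factors term in a repeated-measures ANOVA is the arm difference in each parent's mean over all occasions. A module given after T2 can move only T3 and T4. If the sample size puts the full module effect on the four-occasion mean, it assumes an arm difference at two assessments taken before the module exists for the parent.

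Two things are at stake. The 80% in 8.2 may not describe the test that 8.3 says the trials are powered for. And because 8.3 fixes neither the model nor the time point, contrasts with very different power and different meanings all remain open for the primary result. Section 1.1 narrows this somewhat, but post-test is not tied to T2, T3 or T4, and higher scores is not tied to any occasion.

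**Working it through.** **Inputs.** From 8.1 and 8.2: N = 124 (62 per arm), d = .45, alpha .05, four assessments. From 8.3: between-factors repeated-measures ANOVA. From 7.1, 7.2.1 and 7.2.4: T1 and T2 before the module, T3 and T4 after. Assumed here: two-sided alpha (as in Equation 1 for Incredible Years), SD 1, equal correlation rho between occasions, no clustering, no dropout. The value rho = .7 is carried over from Incredible Years.

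**Formula.** The noncentral F test has lambda = (N/4) × d² / V on (1, 122) degrees of freedom, where V is the variance of the quantity compared. For the mean of four assessments, V = (1 + 3 rho)/4.

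**Step 1: reproduce the 62.** At rho = .7, V = 3.1/4 = .775. Then lambda = 31 × .2025/.775 = 8.10 and power is 80.6%. With 61 per arm, power is 79.97%, so 62 is the smallest size that reaches 80%. Correlations of .5, .6 and .8 would give 50, 56 and 67 per arm.

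**Step 2: put the effect where the schedule allows it.** With differences of 0, 0, .45 and .45, the average is .90/4 = .225. At rho = .7, lambda = 31 × .050625/.775 = 2.025.

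| rho | Power, four-assessment mean, d = .225 |
|---|---|
| 0 | 70% |
| .3 | 44% |
| .5 | 35% |
| .7 | 29% |
| .8 | 27% |

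Variants at rho = .7:
- T2 already carries a quarter of the effect (average 1.0125/4 = .253): 36%.
- T2 already carries half (average 1.125/4 = .281): 42%.
- T4 keeps only half (average .675/4 = .169): between 18% and 19%.

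**Step 3: other contrasts at 62 per arm, rho = .7, constant .45 at T3 and T4.**

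| Contrast | V | lambda | Power |
|---|---|---|---|
| One post-module assessment | 1 | 6.28 | 70% |
| Mean of T3 and T4 | (1 + rho)/2 = .85 | 7.39 | 77% |
| Mean of T3 and T4 adjusted for T1, df (1, 121) | .85 − .49 = .36 | 17.44 | 98.5% |

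The last figure depends on favourable assumptions. It is 94% at rho = .5. If T4 keeps half the effect (mean .3375), it is 87% at rho = .7 and 75% at rho = .5. If the correlation of T1 with T3 and T4 is only .3 to .5 while T3 and T4 correlate at .7 (V = .85 − r²), it is 81% to 89%. Both together give 57% to 67%. Site clustering and dropout would lower every figure.

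No figure is given for Incredible Years. Its calculation uses three occasions, which 8.2 does not identify, and the definition of Delta is not stated.

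**The case against.** The strongest reply is that 8.3 does not commit the trials to testing the four-assessment mean. The sentence on ANOVA is brief, three other families of method are listed, and the 29% may be the power of a test that is never run. This stands, and it is why the 29% is conditional. It does not supply a power statement for whichever contrast is used instead.

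The 62 also has a rival derivation. A one-sided t-test at a single assessment gives 62 as its smallest size (79.6% at 61, 80.1% at 62). The second hypothesis in 1.1 is directional, and t-tests come first in the 8.3 list. But this route ignores the four assessments that 8.2 says must be accounted for and the ANOVA that 8.3 names. The four-assessment route is the better fit, but it is not proven.

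A reader might infer that the power falls short whatever the assumptions. That goes too far. Under a two-sided test with no arm difference at T1 or T2, no non-negative correlation reaches 80%. A one-sided test would reach 80.1% at correlation 0, although only 41% at .7. An arm difference at T2 also cannot be ruled out, since 7.2.1 says that by then "experimental condition providers received their training in the SPSHK module". The variants with a quarter or half of the effect at T2 allow for this in part, and power remains at 36% to 42%.

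Finally, the T3/T4 mean adjusted for T1 is one reasonable choice among several. T3 adjusted for T2, for example, has about 94% power at correlation .7.

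**Conclusion.** The point holds as a mismatch between the test named for sizing and the assessment schedule, together with an unspecified primary contrast. If 62 per arm was derived from the four-assessment mean, as the reproduction suggests, and the .45 arises only at T3 and T4, the two-sided power of that test is about 29% at correlation .7 (44% to 27% for .3 to .8, and 70% at 0). The stated 80% does not apply to it. This rests on equal correlations, no arm difference at T1 and T2, the full .45 at both later assessments, and no clustering or dropout.

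A reader might infer that PAT and SafeCare are underpowered, or that no contrast could have reliable power. The documents support neither. At the same size and correlation, before clustering and dropout, the T3/T4 mean has about 77% power, and about 98.5% when adjusted for T1. Whether 62 per arm is enough is a separate question, which a restated calculation would answer.

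**What to change.** In 8.3, name one post-module primary contrast in place of the four-assessment group effect. One suitable choice is the arm difference in the Module Assessment over T3 and T4, adjusted for the T1 score, in a linear mixed model. T1 is the safer covariate because it precedes all session content, whereas T2 follows sessions led by providers already trained in the module. The model should have a random effect for the unit actually randomized (and for group in Incredible Years), with small-sample degrees of freedom if there are few units.

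Before that, reconcile the unit. Section 7.1 says "Randomization will occur at the site level to reduce the potential for contamination", while section 17.1 describes facilitators being randomized.

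In 8.2, restate PAT and SafeCare power for the chosen contrast. Label and vary the assumptions: sidedness, T3–T4 correlation, T1-to-post correlation, persistence to T4, parents per cluster, intracluster correlation and dropout. For Incredible Years, state which three occasions and which definition of Delta were used, and recompute if any occasion precedes the module.

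The cost is rewording 8.2 and 8.3 and slightly more analysis work. T1, T3 and T4 scores are already collected, so correcting this point needs no new data or participants. The downside is that the restated power rests on assumed values and may come out below 80%.

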9.0 Confidentiality, Privacy and Data Management

For research being conducted at Penn State Hershey or by Penn State Hershey researchers only, the research data security and integrity plan is submitted using “HRP-598 – Research Data Plan Review Form Application Supplement”, which is available in the Library in CATS IRB (<http://irb.psu.edu>). Refer to Penn State College of Medicine IRB’s “Standard Operating Procedure Addendum: Security and Integrity of Human Research Data”, which is available on the IRB’s website. **In order to avoid redundancy, for this section state “See the Research Data Plan Review Form” in section 9.0 if you are conducting Penn State Hershey research and move on to section 10.**

For all other research, in the sections below, describe the steps that will be taken to secure the data during storage, use and transmission.

9.1 Confidentiality

9.1.1 Identifiers associated with data and/or specimens

List the identifiers that will be included or associated with the data and/or specimens in any way (e.g., names, addresses, telephone/fax numbers, email addresses, dates (date of birth, admission/discharge dates, etc.), medical record numbers, social security numbers, health plan beneficiary numbers, etc.).

If no identifiers will be included or associated with the data in any way, whether directly or indirectly, please indicate this instead.

The provider-subjects will provide their name, email, and phone number.

The contact information sheet filled out by participants at the first assessment point asks for their name, address, phone number(s), and email. It also asks for them to identify a friend or family member we can call should we not be able to locate the participant using the information they provide. This is a method members of our team have used previously, and is the best way to prevent loss-to-follow-up. The contact sheet is necessary to ensure participants are reached for later phases of study. The master ID file and contact information sheet are the only documents linking participant ID with identifiable information. The contact information sheet will be collected immediately upon completion by a study team member, before participants fill out the surveys, and placed in a pre-paid, addressed, and sealed envelope. These will be returned to Penn State separately from other survey instruments and immediately following this session.

9.1.1.1 Use of Codes, Master List

If identifiers will be associated with the data and/or specimens (as indicated in section 9.1.1 above), describe whether a master record or list containing a code (i.e., code number, pseudonyms) will be used to separate the data collected from identifiable information, where that master code list will be stored, who will have access to the master code list, and when it will be destroyed.

If identifiers are included or associated with the data as described in section 9.1.1 above, but no master record or list containing a code will be used, it will be assumed by the IRB that the investigator plans to directly link the identifiers with the data.

The research team will randomly assign a pre-generated participant ID to each participant (parent or provider). These are randomly-generated combinations of 5 digits. The project manager will be the keeper of a password-protected file stored on a secured drive that links the name to ID and a file that links name to contact information.

For providers: The consent form will be collected at the time of training and stored separately from any fidelity monitoring data. The hard copies of the consent form will be stored in a locked filing cabinet, separate from fidelity data (containing only IDs), in a locked office, in a swipe-access controlled office suite.

For parents: The consent form and contact information sheet will be collected immediately after completion and stored in a sealed envelope separately from hard copies of surveys. This will be standard practice for all study team members, whether they are PSU team members or affiliates. Upon return to University Park, hard copies of the contact sheet will be stored in a locked filing cabinet, separate from surveys (containing only unique ID codes), in a locked office, in a swipe-access controlled office suite.

Because this study involves longitudinal research requiring continued contact with subjects to maintain participation, personal contact information for enrolled participants will be retained until the study is completed, at which

point they and the master ID file will be destroyed. De-identified electronic information will be stored indefinitely.

Provider fidelity data will be submitted through REDCap. The audio file will not be saved with any identifiable information, only the provider study ID. A separate secure REDCap database will contain the provider name, email, and ID. Another REDCap database will contain the subject ID and audio files.

9.1.2 Storage of Data and/or Specimens

Describe where, how and for how long the data (hardcopy (paper) and/or electronic data) and/or specimens will be stored. NOTE: Data can include paper files, data on the internet or websites, computer files, audio/video files, photographs, etc. and should be considered in the responses. Refer to the “Investigator Manual (HRP-103)” for information about how long research records must be stored following the completion of the research prior to completing this section. HRP-103 can be accessed by clicking the Library link in CATS IRB (<http://irb.psu.edu>).

Please review [Penn State’s Data Categorization Project](#) for detailed information regarding the appropriate and allowable storage of research data collected according to [Penn State Policy AD71](#). Although the IRB can impose greater confidentiality/security requirements (particularly for sensitive data), the IRB cannot approve storage of research data in any way or using any service that is not permissible by [Penn State Policy AD71](#).

Paper surveys will be stored in sealed and signed envelopes during transfer from the field to our secure office space. Penn State study team members will keep such envelopes securely in their possession the entire time from the field to University Park; in the event affiliate staff are collecting data without the presence of a Penn State team member, they will be provided with pre-paid envelopes to mail surveys back to Penn State immediately after the session. Paper surveys will be stored in a locked filing cabinet in a secured office in the Center for Healthy Children on the University Park campus. They will only be accessible to project staff. After surveys have been electronically entered into a database, the hardcopies will be shredded. Electronic data will be stored on a secure server on password-protected computers in locked rooms. Per regulations, electronic data will be kept for 3 years after the close of the study, after which time data will be deleted from our secure server.

Audio recordings will be done on a password-protected smartphone. After the facilitator uploads the audio recording to REDCap, the audio file will be deleted from the recording device. Audio files will be labeled with the provider’s unique 5-digit ID.

After each audio recording has been listened to by the PSU research team through REDCap, the audio recording will then be moved to a storage folder on Box to be maintained along with other research records for 3 years after the closure of the study. Recordings will not be transcribed.

9.1.3 Access to Data and/or Specimens

Identify who will have access to the data and/or specimens. This information should not conflict with information provided in section 9.1.1.1 regarding who has access to identifiable information, if applicable.

Only members of the research team will have access to the data.

9.1.4 Transferring Data and/or Specimens

If the data and/or specimens will be transferred to and/or from outside collaborators, identify the collaborator to whom the data and/or specimens will be transferred and how the data and/or specimens will be transferred. This information should not conflict with information provided in section 9.1.1.1 regarding who has access to identifiable information, if applicable.

In the event affiliate staff collect data without the presence of a Penn State team member to take immediate possession of the data, they will be provided with pre-paid envelopes to mail surveys back to Penn State immediately after the session.

